6.10.1.24 Clinical site subgroup comparison

Sensor Agreement for subjects at the various clinical sites in the study will be compared to determine whether there is any evidence of differences (Table 20 in APPENDIX 1).

6.10.1.25 Effect of rate of change on sensor performance

Sensor Agreement for the different categories of rates of change as displayed by the system will be compared to determine whether there is any evidence of differences (Table 21 in APPENDIX 1).

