11.1.2 Randomization and Data Pooling across sites

Subjects will not be randomized. Subjects will be selected consecutively (i.e., selecting every subject in the order they present at the site) among those who meet the inclusion/exclusion criteria. All subjects will receive sensors and transmitters. The primary effectiveness endpoint (MARD) will be analyzed with data pooling across sites. Site effects will be examined, but only descriptively.

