6.10.1.2 System agreement with reference

The Agreement of the CGM System to reference measurements will be assessed by looking at proportions of all differences $\{ (\text{Glucose})_{\text{SENSOR}} - (\text{Glucose})_{\text{REFERENCE}} \}$ in intervals of $[0 - 20\%]$,

[0-30%], and [0-40%). For readings less than or equal to 80 mg/dL, the absolute difference in mg/dL between the two glucose results will be calculated. For values greater than 80 mg/dL, the absolute percent difference (%) from the reference values will be calculated.

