6.10.1.20 Effect of gender on sensor performance

Sensor Agreement will be stratified by gender and examined to determine whether there is any evidence of differences between genders (Table 16 in APPENDIX 1).

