6.10.1.23 Effect on sensor performance in dominant or non-dominant arm

Sensor Agreement will be stratified by dominant arm and examined to determine whether there is any evidence of differences (Table 19 in APPENDIX 1).

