6.10.1.29 Calibration stability

To demonstrate performance of the system spanning the duration between calibration points, the Sensor performance will be assessed using Agreement in 4-hour increments over the period from 0 to 12 hours (Table 25 in APPENDIX 1).

The example tables that compare the effectiveness endpoints calculated for the three different combinations of 2 generations of hardware and 2 generations of firmware are shown in Appendix 2.

7 References and Supporting Documentation

5. Clinical and Laboratory Standards Institute. Performance Metrics for Continuous Interstitial Glucose Monitoring: Approved Guideline. CLSI Document POCT05-A. Wayne, PA. 2008.
6. In-vitro Diagnostic Test Systems-Requirements for Blood Glucose Monitoring Systems for Self Testing in Managing Diabetes Mellitus. ISO 15197:2003. Geneva.

7. U.S. Food and Drug Administration. The Content of Investigational Device Exemption (IDE) and Premarket Approval (PMA) Applications for Low Glucose Suspend (LGS) Device Systems. Draft Guidance. 2011.
8. U.S. Food and Drug Administration. The Content of Investigational Device Exemption (IDE) and Premarket Approval (PMA) Applications for Artificial Pancreas Device Systems. Draft Guidance. 2011.
9. U.S. Food and Drug Administration. Design Considerations for Pivotal Clinical Investigations for Medical Devices. 2013.
10. Clinical investigation of medical devices for human subjects — Good clinical practice. ISO 14155:2011. Geneva.

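### Rate of change, time since calibration, site, arm and demographic effects are judged only by percent within 20/30/40% of reference, which loses the sign of the error and coarsens its size

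*SAP*

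**What the plan says.** SAP 6.10.1.25 states that "Sensor Agreement for the different categories of rates of change as displayed by the system will be compared". The neighbouring sections follow the same pattern. For gender (6.10.1.20): "Sensor Agreement will be stratified by gender and examined to determine whether there is any evidence of differences between genders". For arm (6.10.1.23): "Sensor Agreement will be stratified by dominant arm and examined to determine whether there is any evidence of differences". For site (6.10.1.24): "Sensor Agreement for subjects at the various clinical sites in the study will be compared to determine whether there is any evidence of differences". Age, BMI, and race and skin color (6.10.1.21, 6.10.1.22, 6.10.1.26) are handled likewise. For calibration stability (6.10.1.29), "the Sensor performance will be assessed using Agreement in 4-hour increments over the period from 0 to 12 hours".

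Agreement is defined in SAP 6.10.1.2. Above 80 mg/dL, "the absolute percent difference (%) from the reference values will be calculated"; at or below 80 mg/dL the absolute difference in mg/dL is used. The sample layouts of Tables 16-22 and 25 carry the number of pairs and the percent within 20/20, 30/30 and 40/40. They carry no MARD, mean relative difference or SD. They also lack the 15/15 column that Tables 6C, 6D, 8 and 10A have.

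Protocol 11.1.2 pools MARD across sites and adds: "Site effects will be examined, but only descriptively".

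**The concern.** The paired error is continuous and signed, and for two of these questions the sign is what matters. The device measures interstitial glucose and is compared with plasma glucose, so a lagging sensor would tend to read low while glucose rises and high while it falls. Table 21 has signed rows, from below -2 to above 2, but no signed outcome. Drift between calibrations also has a direction, and Table 25 cannot show it.

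The SAP reference list includes work on sensing time lag and physiological lag, yet Section 6 plans no lag analysis. These tables are therefore where a reader would look for it.

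For site the point is different. The pooled quantity is MARD, and Table 20 does not show MARD by site. At stake is a report that finds no evidence of differences because the chosen measure responds weakly to modest bias and not at all to its sign.

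**Working it through.** **Nothing to reproduce.** The documents give no expected MARD, effect size or power for these comparisons, and SAP 4.4 says the sample size is not power-based. The figures below show how the measure behaves. They do not predict this trial's results.

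**Assumptions (not in the documents).** Relative error is Normal with bias b and SD s, with s from 9% to 15%. At zero bias MARD = s × √(2/π), which gives 7.18% to 11.97%. Percent error is used throughout. Agreement in fact uses mg/dL at or below 80 mg/dL, which by the table in Protocol 11.1.4 is (815 + 2,194) / 22,786 = 13.2% of expected pairs.

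**Formula.** Percent within k is P(|e| ≤ k) = Φ((k − b)/s) − Φ((−k − b)/s).

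**Step 1: sign.** Replacing b by −b gives Φ((k + b)/s) − Φ((−k + b)/s). Since Φ(x) = 1 − Φ(−x), this equals the original expression. Biases of +b and −b give identical agreement at every cut. Rows biased by +5% and −5% differ by 10 points in mean relative difference and by exactly 0 in all three agreement columns.

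**Step 2: size.** Example with s = 11, k = 20:
- b = 0: Φ(1.818) − Φ(−1.818) = 93.1%.
- b = 5: Φ(1.364) − Φ(−2.273) = 90.2%.
- b = 10: Φ(0.909) − Φ(−2.727) = 81.5%.

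Percent within 20/30/40:

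| s | b = 0 | b = ±5 | b = ±10 |
|---|---|---|---|
| 9 | 97.4 / 99.9 / 100.0 | 94.9 / 99.7 / 100.0 | 86.6 / 98.7 / 100.0 |
| 11 | 93.1 / 99.4 / 100.0 | 90.2 / 98.8 / 99.9 | 81.5 / 96.5 / 99.7 |
| 13 | 87.6 / 97.9 / 99.8 | 84.8 / 96.9 / 99.6 | 76.9 / 93.7 / 98.9 |
| 15 | 81.8 / 95.4 / 99.2 | 79.4 / 94.2 / 98.9 | 72.5 / 90.5 / 97.7 |

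A 5% bias lowers percent within 20 by 2.4 to 2.9 points, within 30 by 0.2 to 1.2, and within 40 by at most 0.3. A 10% bias lowers percent within 20 by 9.3 to 11.6 points. The 30 and 40 columns start at 95.4% or higher, so they have little room to move.

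**Step 3: a lag of plausible size.** Assume the Table 21 categories are in mg/dL per minute, glucose changes at 2 mg/dL/min, the delay is 5 to 10 minutes and the level is 150 mg/dL. The error is 10/150 to 20/150, or 6.7% to 13.3%. Percent within 20 then falls by 4 to 5 points at the low end and 16 to 20 at the high end, equally in the rising and falling rows.

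**Step 4: bias against scatter.** With s = 11 a 10% bias gives 81.5% within 20. An unbiased sensor with s = 15.1 gives the same 81.5%, and the two give 96.5% and 95.3% within 30. The table cannot readily tell them apart.

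**Step 5: information lost (illustration only, since no test is planned).** Take independent pairs, two-sided 5% and 80% power. Separating a 5% bias from none needs 51 to 142 pairs per group on the signed mean and 984 to 4,260 on percent within 20, about 19 to 30 times as many. For a 10% bias the figures are 13 to 36 and 99 to 321. Pairs within a subject are correlated, so only the ratios are of interest.

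**Step 6: MARD alone does not repair this.** MARD is also unsigned. A 5% bias raises it by only 0.66 to 1.08 points. The signed mean is the column that answers Tables 21 and 25.

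**The case against.** The strongest reply is that much of the information exists elsewhere and that nothing formal depends on these tables. Several parts of it stand.

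- **Sensor life.** Signed mean relative difference is planned cumulatively and by 30-day interval (SAP 6.10.1.10, Tables 11A and 11B), and SAP 6.10 repeats the exploratory analyses by clinic visit day. A reader might infer that drift is unexamined. That is not so; the gap is drift between calibrations.
- **MARD by group.** It is planned by medication (Table 24), night and day (Table 10A) and hardware/firmware (Table 2.2).
- **Arm.** Table 9 gives the signed mean difference between the two sensors, and Tables 2.2 and 2.3 give signed error by transmitter. The left arm carries Gen 1 and the right Gen 2, so a between-arm bias would show, though confounded with transmitter and not split by dominance.
- **Size.** It is reduced to three cuts, not thrown away. Table 21 has a flat row, so a large lag would appear as both outer rows falling below it.
- **Site.** The Protocol promises only a descriptive look and names no measure. Table 20 does not contradict it.
- **Descriptive status.** The layouts are samples and no hypothesis is tested. Detection rates from tests would describe a procedure the plan does not run.

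The plan may also follow a customary reporting format. The documents cite a performance-metrics guideline, but its content cannot be judged from them, so no weight is placed on a missing justification.

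None of this supplies a signed error by rate of change or time since calibration, or MARD by site. A descriptive plan depends wholly on what its tables display.

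**Conclusion.** The point holds in a limited form. For rate of change and time since calibration, the plan asks a directional question with a measure that cannot show direction. For site, arm and demographics it uses a measure that barely registers modest bias. Under the assumed SD of 9-15%, a 5% bias costs 2.4 to 2.9 points of percent within 20, and a 10% bias costs 9.3 to 11.6 points with no indication of sign.

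A reader might infer that lag, drift or site effects would be invisible altogether. The documents do not support that: effects of about 10% or more would lower agreement visibly, and drift over sensor life has its own signed analysis.

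The loss of sign follows from the definition of Agreement together with symmetric scatter. The sizes rest on the normal model and the assumed SDs. The effectiveness endpoint is untouched and no decision rule is affected. The change is worth making because it is cheap and uses measures the SAP already defines.

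**What to change.** - **Tables 21 and 25 (SAP 6.10.1.25 and 6.10.1.29).** Add signed mean relative difference, with mean difference in mg/dL for reference values of 80 mg/dL or less as in the footnote to Table 6A, and MARD. State in the text that the signed mean difference is the measure of the rate-of-change and calibration-age effect.
- **Table 20 (6.10.1.24).** Add the same two columns, so that site effects appear on the endpoint that is pooled across sites.
- **Tables 16-19 and 22 (6.10.1.20 to 6.10.1.23 and 6.10.1.26).** Add the same columns for consistency with Table 24, which already compares medication groups on MARD.
- Keep the agreement columns and keep all results descriptive.

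The cost is a few sentences of SAP text and a few columns in eight tables. Both measures are already defined in SAP 6.9 and 6.10.1.10, and no new data are collected.

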6.10.1.26 Effect of race skin color on sensor performance

Sensor Agreement will be stratified by race and skin color categories and examined to determine whether there is any evidence of differences between groups (Table 22 in APPENDIX 1).

6.10.1.27 CGM satisfaction survey analysis

CGM satisfaction survey results will be tabulated (Table 23 in APPENDIX 1).

6.10.1.28 Effect of medications

The potential effects (interference) of common medications (e.g., insulin, oral hypoglycemic agents) taken by diabetic subjects on Senseonics CGM accuracy will be evaluated by examining the effectiveness endpoint results (MARD) between patients taking these medications throughout the study (i.e., at screening and upon explant) and not taking these medications throughout the study (Table 24 in APPENDIX 1).

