4.6 Sensor Accuracy (Sampling) Daytime Visits

Visit 6 – Day 30 Accuracy (Sampling) Visit (± 7 Days)

Visit 7 – Day 60 Accuracy (Sampling) Visit (± 7 Days)

Visit 8 – Day 90 Accuracy (Sampling) Visit (-3/+7 Days)

	Approximate Visit	Approximate Sampling
Visit 6 (Day 30 ± 7 Days)	14 hours	12.5 hours
Visit 7 (Day 60 ± 7 Days)	14 hours	12.5 hours

Visit 8 (Day 90 -3/+7 Days)	15 hours	12.5 hours
-----------------------------	----------	------------

Approximate visit timeline:

Approximate time	Activity	Time relative to first IV sample
~07:00	Admission	T=0 -1:00
~07:15-07:45	Period for glucose stabilization and CGM calibration	T=0 -0:45 - -0:15
~08:00	First IV blood sample drawn	T=0 0:00
~08:00 – 13:00	
For qualifying subjects, hypoglycemia challenge to achieve hypoglycemia target <60 mg/dL.
 
 Sampling q 5 min when glucose \leq 75 mg/dL. Target 24 YSI values <75 mg/dL including 6 YSI values <60 mg/dL at q 5 min before rescue. Subjects fed low glycemic meal. 	T=0 0:00 – +5:00
~08:00 – 13:00	
 Alternatively, for qualifying subjects, hyperglycemia challenge to achieve hyperglycemia to goal glucose >350 mg/dL. Sampling @ 5 min when glucose \geq 325 mg/dL, with a target duration of 1 hour. Challenge may be stopped once 12 samples ≥ 325 mg/dL are collected. 	T=0 0:00 – +5:00
~08:00 – 13:00	For those subjects not following a basal/bolus routine on MDI or CSII, glucose control will be free range.	T=0 0:00 – +5:00
~09:00	Fingerstick blood glucose	T=0 +1:00
~10:00	Fingerstick blood glucose	T=0 +2:00
~11:00	Fingerstick blood glucose	T=0 +3:00
~12:00	Fingerstick blood glucose	T=0 +4:00
~13:00	Fingerstick blood glucose	T=0 +5:00
~13:00-16:00	Recovery Period with meal/bolus and glucose stabilization	T=0 +5:00 - +8:00
~16:00-19:30	Free range glucose control	T=0 +8:00 - +11:30
~14:00	Fingerstick blood glucose	T=0 +6:00
~15:00	Fingerstick blood glucose	T=0 +7:00

Approximate time	Activity	Time relative to first IV sample
~16:00	Fingerstick blood glucose	T=0 +8:00
~17:00	Fingerstick blood glucose	T=0 +9:00
~18:00	Fingerstick blood glucose	T=0 +10:00
~19:00	Fingerstick blood glucose	T=0 +11:00
~19:30-20:30	Discharge preparation period	T=0 +11:30 - +12:30
~20:00	Blood draw for dexamethasone	T=0 +12:00
~20:30	Last IV blood sample drawn	T =0 + 12:30
21:00	Discharge	T=0 +13:00

The following procedures/instructions will be followed for accuracy (sampling) daytime visits at days 30, 60 and 90:

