5.12.1 Subject eligibility

Subjects with gastroparesis will not be eligible to participate in glucose challenges. Subjects not on insulin therapy will not be expected to undergo hypoglycemic challenges. Eligible subjects will be required to participate in glucose challenges.

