6.9.1.1 Effectiveness Endpoint: Criteria

The effectiveness objective is to descriptively document the distribution of absolute relative difference across all evaluable subjects and to estimate the MARD. The MARD will be estimated initially when all the subjects complete 30 days of Sensor use for the interim analysis, followed by the MARD based on all the follow-up data through 90 days of Sensor use. Descriptive statistics will be provided for the MARD. There is no hypothesis to be tested. No inferential statistical analysis will be performed.

The effectiveness endpoint is the mean absolute relative difference (MARD), defined as the average of absolute difference of paired Senseonics CGM System and reference glucose readings divided by the reference glucose reading (reference) for all reference glucose values, that is:

$$\text{MARD} = \left(\left(\sum \frac{|(\text{Glucose})_{\text{SENSOR}} - (\text{Glucose})_{\text{REFERENCE}}|}{(\text{Glucose})_{\text{REFERENCE}}} \right) / n \right) \times 100\%,$$

Where, n is the total number of CGM and reference glucose pairs during the evaluation period, that is, after 30 days of Sensor use for the interim analysis, and after 90 days of use for the final analysis.

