Table 16. Effect of Gender on System and Reference Agreement (sample table)

Gender	Number of Paired Senseonics CGM and Reference	Percent within 20/20% Reference	Percent within 30/30% Reference	Percent within 40/40% Reference
M				
F				

Table 17. Effect of Age on System and Reference Agreement (sample table)

Age	Number of Paired Senseonics CGM and Reference	Percent within 20/20% Reference	Percent within 30/30% Reference	Percent within 40/40% Reference
18-20				
21-44				
45-65				
Over 65				

Table 18. Effect of BMI on System and Reference Agreement (sample table)

BMI	Number of Paired Senseonics CGM and Reference	Percent within 20/20% Reference	Percent within 30/30% Reference	Percent within 40/40% Reference
< 25				
[25, 30)				
≥ 30				

Table 19. Effect of Dominant Hand on System and Reference Agreement (sample table)

Dominant Hand (Y/N)	Number of Paired Senseonics CGM and Reference	Percent within 20/20% Reference	Percent within 30/30% Reference	Percent within 40/40% Reference
Y				
N				

Table 20. Effect of Clinical Site on System and Reference Agreement (sample table)

Site Number	Number of Paired Senseonics CGM and Reference	Percent within 20/20% Reference	Percent within 30/30% Reference	Percent within 40/40% Reference
1				
2				
3				

Table 21. Effect of Rate of Change on System and Reference Agreement (sample table)

System Rate of Change	Number of Paired Senseonics CGM and Reference	Percent within 20/20% Reference	Percent within 30/30% Reference	Percent within 40/40% Reference
<-2				
[-2,-1)				
[-1,1]				
(1,2]				
>2				

Table 22. Effect of Race or Skin Color on System and Reference Agreement (sample table)

Race and Skin Color Category	Number of Paired Senseonics CGM and Reference	Percent within 20/20% Reference	Percent within 30/30% Reference	Percent within 40/40% Reference
Race and Skin Color Category 1				
Race and Skin Color Category 2				
Race and Skin Color Category 3				

Table 23: CGM Satisfaction Survey Results (sample table)

Survey Questions	Agree Strongly (N/%)	Agree (N/%)	Neutral (N/%)	Disagree (N/%)	Disagree Strongly (N/%)
Question 1					
Question 2					
⋮					
Question N					

Table 24. Effect of Medications (sample table)

Class of Medication	Subjects Taking Medication	MARD with Medication [mean (SD) / n]	MARD with No Medication [mean (SD) / n]	P-value
Diabetes Medication				
Thyroid Medication				
Hypertension Medication				
Cholesterol Medication				

Table 25. Calibration Stability (sample table)

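### The medication-interference comparison of overall MARD is confounded, for insulin and oral agents, by challenge participation that depends partly on insulin regimen

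*SAP*

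**What the plan says.** SAP 6.10.1.28 sets out to evaluate possible interference from "common medications (e.g., insulin, oral hypoglycemic agents) taken by diabetic subjects". The method is "examining the effectiveness endpoint results (MARD) between patients taking these medications throughout the study" and subjects not taking them. No stratification or adjustment is mentioned.

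MARD is defined in SAP 6.9.1.1 as an average over pairs, in which "n is the total number of CGM and reference glucose pairs during the evaluation period". Every pair counts equally.

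The shell, Table 24 in SAP Appendix 1, has a "Class of Medication" column with four entries (diabetes, thyroid, hypertension, cholesterol), MARD with and without the medication, and a P-value. It has no glucose-range or challenge rows.

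The protocol decides who is challenged:
- Section 5.12.1: "Subjects not on insulin therapy will not be expected to undergo hypoglycemic challenges". It also says: "Subjects with gastroparesis will not be eligible to participate in glucose challenges".
- Section 4.6 (Visits 6 to 8): "For those subjects not following a basal/bolus routine on MDI or CSII, glucose control will be free range". Sections 4.4.12 and 4.4.13 apply the same rule to both challenges at Visit 3.
- Section 4.5.14 (Visits 4 and 5) refers only to qualifying subjects and gives no regimen rule.

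Section 5.9.2 sets sampling every 5 minutes at or below 75 mg/dL and at or above 325 mg/dL, and every 15 minutes in between.

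**The concern.** The challenges exist to widen the glucose range observed (Protocol 5.12), and dense sampling gives those extremes extra weight in a pair-weighted mean. If percent error differs between low, middle and high glucose, a group with more induced lows and highs will have a different overall MARD even with identical sensors and no drug effect. Because challenge participation depends partly on insulin regimen, that difference falls on the two drug classes the SAP names.

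A glucose-mix artefact could then be reported as interference, or could mask it. Table 24 would attach a P-value, although SAP 6.10 allows only descriptive statistics for exploratory outcomes. Tables 16 to 22 use 20/20-type agreement, which SAP 6.10.1.2 expresses in mg/dL at or below 80. Among these subgroup tables and Table 24, only Table 24 uses MARD.

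**Working it through.** **1. Reproduce the protocol's sampling figures.**
- Hypoglycemia challenge (5.12): 120/5 + 1 = 25 points below 75 mg/dL; 30/5 + 1 = 7 below 60.
- Hyperglycemia challenge (5.12): 60/5 + 1 = 13 points above 325 mg/dL; 13 + 60/15 = 17 above 180.
- Visits 3 to 5 (Section 4 schedule): 13×4 + 3×12 + 1 = 89 samples.
- Visits 6 to 8: 11.5×4 + 1×12 + 1 = 59 samples.

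All agree with the documents.

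**2. Glucose mix by design, per sensor, at full challenge yield.**
- Challenged subject: 3×89 + 3×59 = 444 samples. Visits 3 to 5 give 3×25 = 75 low and 3×13 = 39 high points. Each of Visits 6 to 8 adds 25 low or 13 high. The totals are 75 to 150 low (17% to 34%) and 39 to 78 high (9% to 18%).
- Free-range subject sampled every 15 minutes throughout: 3×(16×4 + 1) + 3×(12.5×4 + 1) = 3×65 + 3×51 = 348 samples, with no induced lows or highs.

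**3. MARD difference with no interference.** MARD = (low×a + mid×b + high×c)/total, with the same a, b, c in both groups. Assumptions:
- a = 12% to 25% below 75 mg/dL, b = 9% to 10% mid-range, c = 8% to 10% above 325.
- Visits 6 to 8 split evenly between the two challenges: 112.5 low, 58.5 high, 273 mid.
- The free-range group has 0% to 5% spontaneous lows and 2% highs.

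Results:
- a/b/c = 15/10/8, no spontaneous lows: challenged (1687.5 + 2730 + 468)/444 = 11.0%; free range 0.98×10 + 0.02×8 = 10.0%. Difference 1.0 point.
- Smallest (12/10/8, 5% lows): 4548/444 = 10.24 against 10.06. Difference 0.2.
- Largest (25/9/8, no lows): 5737.5/444 = 12.92 against 8.98. Difference 3.9.
- With half the challenge points and the total held at 444: 0.1 to 2.0.
- If the comparison group also has the hyperglycemia challenge at Visits 3 to 5: about 0.35 to 4.0.

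The even split matters. If all three daytime challenges were hyperglycemic, the low end becomes 4434/444 − 10.06 = −0.07. If all three were hypoglycemic, the high end becomes 6357/444 − 8.98 = 5.3.

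The 59-sample figure allows only one hour of dense sampling. A full daytime hypoglycemia challenge would need 10.5×4 + 2×12 + 1 = 67. Using 67 where it applies gives a total of 456 and changes the 11.0% above only in the second decimal (11.00 to 10.98).

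**4. Check against the expected pairs in Protocol 11.1.4.** Pairs at or below 80 mg/dL: 815 + 2194 = 3009 of 22786 (13.2%). Pairs above 300: 623 + 319 = 942 (4.1%). Assume 18% low, 11% mid and 8% high, and an all-mid-range comparator. The excess is 0.132×(18 − 11) − 0.041×(11 − 8) = 0.8 points. Low-range values of 15% and 25% give 0.4 and 1.7. This mix averages over all planned sensors, so challenged subjects could lie above it.

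**5. After the change.** Under the same assumption of equal accuracy within each band, a comparison within bands gives a difference of 0 by construction.

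**The case against.** The analysis is one of many exploratory items, is labelled descriptive, has no decision rule and cannot move the main endpoint. SAP 6.10 asks for results by visit day, and Tables 6A to 6F show accuracy by glucose range. Table 24 is a sample shell and the drugs in the text are examples, so the final rows are not fixed. The low consequence stands, and so does the status of the shell. The by-visit and by-range tables do not repair this contrast: challenge status differs between subjects within a visit, and the range tables are not split by medication.

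Several stronger readings are tempting but not supported:
- *Only insulin users are challenged, so the contrast simply measures who was challenged.* The rule is clear for hypoglycemia challenges only. For hyperglycemia, Protocol 4.4.12 and 4.6 restrict by regimen, 5.12.1 does not bar subjects for not being on insulin, and 4.5.14 is silent. Insulin users outside a basal/bolus routine at Visits 3 and 6 to 8, and those with gastroparesis, are also unchallenged. Even at full yield, points below 75 or above 325 mg/dL are a minority of pairs.
- *The artefact is 1.5 to 5.1 points.* That is one daytime hypoglycemia session at full yield: (24×a + 42×11)/66 − 11 for a = 15% to 25%. Table 24 pools all visits.
- *The mg/dL rule at or below 80 shows that the SAP recognised inflated percent error.* The Table 6A footnote gives no reason.
- *The no-medication arm of the diabetes row will be almost empty.* This is plausible, since diabetes of at least one year is required, but the documents give no medication-use figures.
- *Insulin will be reported as harmful and oral agents as protective.* With its single diabetes row, the present shell cannot show either result.

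**Conclusion.** The concern holds as confounding. For insulin and oral hypoglycemic agents, the unadjusted MARD contrast mixes any drug effect with differences in glucose mix and sampling density that follow partly from insulin regimen, and also with diabetes type. With no interference, the offset is about 0.2 to 3.9 MARD points over the study, 0.1 to 2.0 at half yield, and about 0.8 with the protocol's pair mix and 18/11/8% accuracy. Size and direction depend on band-specific accuracy, challenge yield and the daytime challenge split, none of which the documents fix. Some offset is expected whenever percent error differs by glucose range and the groups' mixes differ.

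Separately, the insulin and oral-agent contrasts named in the text have no rows in Table 24, and Protocol 4.4.12, 4.5.14, 4.6 and 5.12.1 differ on who receives the hyperglycemia challenge. The main MARD endpoint is unaffected.

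**What to change.** In SAP 6.10.1.28 and Table 24:
1. Present the medication contrast within YSI glucose ranges, with all ranges shown and differences in mg/dL at or below 80 as in Table 6A.
2. Add a supporting row restricted to pairs at 81-180 mg/dL outside challenge periods. It should not replace the other ranges, because interference at low or high glucose would then go unseen.
3. Replace the Diabetes Medication row by separate rows for insulin and for oral hypoglycemic agents.
4. State that confounding by diabetes type and regimen remains.

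The protocol passages on hyperglycemia-challenge participation (4.4.12, 4.5.14, 4.6, 5.12.1) must be reconciled, and the P-value column squared with the descriptive-only rule.

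The cost is SAP wording and a revised shell, with no new data. The price is fewer pairs per row.
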